## 3 STUDY TREATMENT, CONDUCT, WITHDRAWAL – CORE

### 3.1 Study Treatment

Module-specific study treatment details are outlined in Section 5.2 (Module 1) Section 5.3 (Module 2) and Section 5.4 (Module 3).

Additional modules may be added at a later date (following a protocol amendment) to investigate combinations with anti-cancer treatments, and to investigate the effects of dosing with and without food on RXC004 PK parameters. RXC004 will be given as a flat dose at each dose level, based on a 60 Kg patient. Eligible participants will be enrolled in sequential cohorts treated with study treatment, while being monitored for safety and DLTs.

During the dose escalation, patients will receive a single dose on the first day of dosing (Cycle 0, Day 1) followed by a washout of 6-10 days for the assessment of PK, then once daily (Modules 1 and 2) or scheduled (Module 3) dosing from Cycle 1 onwards. Patients may continue to receive the study treatment until progression, unacceptable toxicity or withdrawal. Dose levels will not be weight adjusted.

### **3.1.1.2 Free-Drug Exposure Required for Efficacy in Pre-clinical Studies**

The proposed new starting dose of 0.5 mg QD (or a dose and schedule that provides equivalent exposure) should provide free exposure of approximately 2 times the pharmacological  $IC_{50}$  over the dosing interval, based on the PK from Patient 001/001 and assuming dose linearity. This  $C_{min}$  cover is a similar starting point to the cover originally expected for the 10 mg dose based on original predictions from preclinical species and *in vitro* assays (Capan-2 proliferation  $IC_{50}$ ).

In pre-clinical models of cancer, RXC004 has achieved significant tumour-growth inhibition with the free exposure range of 1 x  $IC_{50}$   $C_{min}$  to 10 x  $IC_{50}$   $C_{min}$ . The proposed starting dose should be within this range of  $C_{min}$  exposures and thus we expect to deliver potential patient benefit.

### **3.1.1.3 Free Exposure over $IC_{50}$ Achieved by Competitor PORCN Inhibitors**

The Novartis PORCN inhibitor WNT974 has been dosed in patients between 5 mg QD and 30 mg QD {Janku, 2020 Ref 19}. These doses of WNT974 produce free exposure at  $C_{min}$  of between 3 x and 24 x the pharmacological  $IC_{50}$  of the compound and additionally a higher  $C_{max}$  and AUC than expected for RXC004 0.5 mg. WNT974 was well tolerated in this study and did not reach an MTD.

The A-Star PORCN inhibitor ETC-159 has been dosed at a range of 1–30 mg QOD in an ongoing Phase 1a/b clinical trial. Phase 1a has completed. {Ng, 2017 Ref 30}. ETC-159 has

an MTD defined as 30 mg QOD ( $C_{\min}$  free exposure  $>50 \times IC_{50}$ ), two of five patients dosed at 30 mg experienced fragility fractures while no fractures were observed at any of the lower doses. A dose of 16 mg QOD ( $C_{\min}$  free exposure  $\sim 20 \times IC_{50}$ ) has been selected for evaluation in Phase 1b.

By modelling the published PK data with both ETC-159 and WNT974 we have demonstrated that RXC004 dosed at 0.5 mg, will result in significantly less exposure than both ETC159 at 16mg and WNT974 at 10 mg, both of which were tolerated doses in man.

The starting dose/schedule of further modules will be the decision of the SRC based on emerging safety and tolerability data, however, will not exceed the equivalent maximum exposure found to be tolerated in Module 1 at that point. Dose increments will be guided by safety data observed during Cycle 1, as well as on-going assessment of safety beyond Cycle 1 in earlier cohorts, plus PK and pharmacodynamic data as available. Every new dose cohort will be evaluated for the occurrence of a DLT during Cycle 1 of treatment.

Based on emerging data, including available biomarker data and/or safety data and/or pre-clinical data, the SRC may consider alternative treatment schedules or dose intervals (for example, twice daily dosing or intermittent treatment), in consultation with the Sponsor. Please refer to the IB and relevant study protocol module for further details.

### 3.1.2 Dose Escalation Scheme (Modules 1 and 2)

RXC004 starting dose and dose-escalation plans for Module 1 are in Section 5.2. The details for the starting dose of RXC004 in combination with nivolumab and dose-escalation plans are in Section 5.3.

Dose, frequency and schedule in subsequent cohorts may increase or decrease in response to safety, tolerability, PK and emerging non-clinical data. There will be no intra-patient dose escalations.

Every new dose cohort will be evaluated for the occurrence of a DLT during Cycle 1 of study treatment. Dose escalation and de-escalation will follow a standard '3+3' scheme for Modules 1 and 2. There will be no dose escalations in Module 3. If no DLT is observed in a cohort, then dose escalation may occur.

#### Cohort Expansion

If one patient experiences a DLT in a group of 3 or more evaluable patients, then the cohort will be expanded to include 6 evaluable patients. Note: cohort expansion to more than 3 patients per cohort ( $\geq 4$  patients) may occur also if more than 3 patients are screened in a single cohort and are deemed eligible; in such cases dose escalation to the next higher dose will not occur until all patients (e.g. 3 or 4 patients) have completed the DLT assessment period with no DLT observed. If only one DLT is observed in the complete cohort of 6 evaluable patients, then dose escalation may occur, once all patients in the expanded cohort have completed their first cycle of treatment with RXC004. If 2 or more patients experience a DLT in a group of up

to 6 evaluable patients (including those in the dose expansion arms), irrespective of the number of patients enrolled, the dose will be considered not tolerated and recruitment to the cohort and dose escalation will cease. A lower, intermediate dose (de-escalation) may be considered in order to better define the MTD.

The highest dose where  $\leq 1$  DLT is seen in 6 patients will be termed the MTD.

If a patient becomes unevaluable following dose administration they may be replaced, if required, to ensure at least 3 patients are evaluable for an assessment of safety and tolerability at that dose. There will be no minimum time period required between completion of dosing in the last evaluable patient from one cohort and the start of dosing in the subsequent cohort.

After each dose level during the dose escalation phase of the study, a SRC will evaluate the safety and tolerability and pharmacokinetics of RXC004 to decide the next dose and/or schedule.

### **3.1.3 Definition of Maximum Tolerated Dose (Modules 1 and 2)**

A dose will be considered non-tolerated and dose escalation will cease if 2 or more of up to 6 evaluable patients experience a DLT at a dose level. Once the non-tolerated dose is defined the MTD may be confirmed at the previous dose-level below the non-tolerated dose or a dose between the non-tolerated dose and the last tolerated dose may be investigated.

Definition of Evaluable Patient for Modules 1 and 2

For decisions on dose escalation, an evaluable patient is defined as a patient who has received study treatment and either:

- Has completed minimum safety evaluation requirements and has received 100% of the specified RXC004 dose in Cycle 0 and at least 66% of the intended dose of RXC004 during Cycle 1 (Patients in Module 2 must also receive 100% of the nivolumab infusion on Cycle 1 Day 1)
- Has experienced a DLT during Cycle 0 and/ or Cycle 1

Any patient that is withdrawn and is not evaluable will be replaced to ensure a minimum number of evaluable patients.

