### 5.2.6 Dose-Limiting Toxicity for Module 1 (RXC004 Monotherapy)

The DLT assessment period runs from the start of dosing with RXC004 (Cycle 0 Day 1) up to Cycle 1 Day 21 for patients enrolled in Module 1.

A DLT is defined as an AE or abnormal laboratory value that occurs from the first dose of study treatment up to Cycle 1 Day 21, assessed as unrelated to disease progression, intercurrent illness, or concomitant medications that despite optimal therapeutic intervention meets any of the following criteria:

1. Haematological toxicity that is:
  - CTCAE  $\geq$  Grade 4 present for more than 4 consecutive days
  - Grade 3 neutropenia (ANC  $\geq$  500 to  $<$  1000 cells/mm^3) of any duration accompanied by fever ( $\geq$  38.5°C) and/or systemic infection
  - Grade 3 thrombocytopenia (25,000 to  $<$  50,000/mm^3) with clinical evidence of bleeding
2. Any other confirmed haematological toxicity CTCAE  $\geq$  Grade 4 (a repeat may be required for confirmation of an isolated abnormality in the absence of clinical signs, symptoms or other abnormal investigations, i.e. a suspected spurious value)
3. Non-haematological toxicity CTCAE  $\geq$  Grade 3 including:

- Laboratory abnormalities that are considered clinically significant by the investigator (with or without clinical symptoms or signs)
  - QTc prolongation ( $> 500$  msec or 60 msec above baseline)
4. Any other toxicity that:
- Is greater than that at baseline, is clinically significant and/or unacceptable, and is judged to be a DLT by the SRC
  - Is a protocol defined stopping criterion and is suspected to be RXC004 related
  - Results in an interruption of dosing schedule of more than 14 days

A DLT excludes:

1. Inadequately treated  $\leq$ Grade 3 nausea and/or vomiting and  $\leq$ Grade 3 diarrhoea
2. Any toxicity clearly unrelated to RXC004 e.g. solely related to the disease or disease-related process under investigation
3. Isolated laboratory changes of any grade without clinical sequelae or clinical significance

The incidence and type of DLT-type toxicity emerging from treatment beyond Cycle 1 Day 21 will be taken into account by the SRC in determining dose-escalation steps.

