### **5.3.6 Dose-Limiting Toxicity for RXC004 + Nivolumab Combination (Module 2)**

The DLT assessment period runs from the start of dosing with RXC004 and nivolumab (Cycle 1 Day 1) up to Cycle 1 Day 28 where nivolumab treatment is administered every 28 days starting on C1D1.

A DLT is defined as an AE or abnormal laboratory value that occurs from cycle 1 day 1 up to Cycle 1 Day 28, assessed as unrelated to disease progression, intercurrent illness, or concomitant medications and is possibly related to RXC004, nivolumab or both agents and that despite optimal therapeutic intervention meets any of the following criteria;

1. Haematological toxicity that is:
  - $\geq$  CTCAE grade 4 neutropenia present for more than 4 consecutive days
  - Grade 3 neutropenia ( $ANC \geq 500$  to  $< 1000$  cells/mm^3) of any duration accompanied by fever  $\geq 38.5^{\circ}C$  and/or systemic infection
  - Grade 3 thrombocytopenia ( $25,000$  to  $< 50,000/mm^3$ ) with clinical evidence of bleeding
2. Any other confirmed haematological toxicity  $\geq$  CTCAEv4 grade 4 (a repeat may be required for confirmation of an isolated abnormality in the absence of clinical signs, symptoms or other abnormal investigations, i.e. a suspected spurious value)
3. Non-haematological toxicity  $\geq$  CTCAE grade 3 including:

- Laboratory abnormalities that are considered clinically significant by the investigator (with or without clinical symptoms or signs)
  - QTc prolongation (> 500 msec or 60 msec above baseline)
4. Any other toxicity that:
    - Is greater than that at baseline, is clinically significant and/or unacceptable, and is judged to be a DLT by the SRC
    - Is a protocol defined stopping criteria and is suspected to be RXC004 or Nivolumab related
  5. Any grade 3 or higher immune-related adverse events

A DLT excludes:

1. Inadequately treated grade  $\leq 3$  nausea and/or vomiting and grade  $\leq 3$  diarrhoea
2. Any toxicity clearly unrelated to RXC004 and/or Nivolumab e.g. solely related to the disease or disease-related process under investigation.
3. Isolated laboratory changes of any grade without clinical sequelae or clinical significance

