**Table 6 Module 2 Dose Interruption and Stopping Criteria**

Event	Action

Colitis events            (e.g. Colitis, ileitis, enterocolitis etc)
	

Grade 1
	
If receiving RXC004, either as monotherapy or in combination with nivolumab;            Reduce RXC004 to a lower dose and manage as per Appendix 5 (and Appendix 8 if applicable)

Grade 2
	
If receiving RXC004, either as monotherapy or in combination with nivolumab            Interrupt RXC004. Manage as per Appendix 5 and Appendix 8 if applicable. When event has resolved to Grade <math>\leq 1^a</math> and steroids tapered to <math>\leq 10</math> mg of prednisone per day (or equivalent), resume RXC004 at a lower dose and nivolumab (if applicable) at 480 mg once every month.            If event re-occurs after re-starting study treatment, then RXC004 and nivolumab (if applicable) should be permanently discontinued.

Grade 3
	
If receiving RXC004 monotherapy;            Interrupt RXC004. Manage as per Appendix 5 When event has resolved to Grade <math>\leq 1^a</math> and steroids tapered to <math>\leq 10</math> mg of prednisone per day (or equivalent), resume RXC004 at a lower dose.            If event re-occurs after re-starting study treatment, then RXC004 should be permanently discontinued.              If receiving RXC004 in combination with nivolumab; permanently discontinue both agents and manage as per Appendix 5 and Appendix 8.

Event	Action
Grade 4	If receiving RXC004, either as monotherapy or in combination with nivolumab; Permanently discontinue study treatment (both agents if applicable). Manage as per Appendix 5 and Appendix 8
Dysgeusia events	
Grade 1 or 2	RXC004 related; Consider dose reduction, depending on clinical symptoms Manage as per Appendix 6 Interrupt RXC004 treatment if dysgeusia is associated with >5kg weight loss from baseline
Grade 2 associated with a 10-20% decrease in body weight	RXC004 related; Manage as per Appendix 6 Reduce RXC004 to a lower dose.
Grade 2 associated with a >20% decrease in body weight	RXC004 related; Manage as per Appendix 6 Permanently discontinue RXC004. Nivolumab can continue if clinical benefit is judged by investigator for a maximum of 12 months total treatment.
Other adverse events	
Any event that meets discontinuation criteria for nivolumab (see Appendix 8)	Permanently discontinue nivolumab. RXC004 can continue, if clinical benefit is judged by investigator.

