### Management:

Monitoring of CRP or fecal calprotectin levels may help to monitor the response to treatment.

Grade	Management
Grade 1 colitis (asymptomatic but evidence on CT scan)	Continue RXC004 at a lower dose and repeat the CT scan within 4 weeks. No action is needed for nivolumab.  No additional treatment is indicated. If the Grade 1 colitis is evident on the second scan despite the lower dose of RXC004, it should be managed as Grade 2 colitis and the scan should be repeated within 4 weeks

Grade	Management
Grade 2 colitis (abdominal pain, mucus or blood in stool)	
Pause RXC004 (and nivolumab if applicable)
 
Manage with corticosteroids at a dose of 0.5mg/kg methylprednisolone equivalent.
 
When symptoms have resolved, taper over 2-4 weeks.
 
If symptoms recur during tapering, the steroid dose may need to be increased again.
 
If no improvement in 72 hrs despite treatment, treat as Grade 3
 
RXC004 can be restarted at a lower dose after colitis has resolved to Grade <math>\leq 1^*</math> and steroids tapered to physiological levels (<10mg prednisone per day equivalent dose) over at least 1 month.
 
If steroids cannot be tapered to physiological levels within 12 weeks of commencing steroid treatment, then RXC004 (and nivolumab if applicable) should be permanently discontinued.

Grade 3 colitis ( severe or persistent abdominal pain, fever, ileus; peritoneal signs)	
Pause RXC004 (and nivolumab if applicable)
 
Seek specialist advice
 
Manage with corticosteroids at a dose of 1mg/kg methylprednisolone equivalent.
 
When symptoms improve, taper steroids to physiological levels over 4-8 weeks and consider use of prophylactic antibiotics and anti-fungals
 
If the patient is receiving RXC004 as a monotherapy, RXC004 can be restarted at a lower dose after colitis has resolved to Grade <math>\leq 1^*</math> and steroids tapered to

Grade	Management

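### In Module 2 a patient held for a related, unlisted toxicity can become non-evaluable and be replaced with no DLT ruling required, while the SAP puts DLT percentages on the Safety Population

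*Protocol*

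**What the plan says.** Protocol 3.1.3 makes a Module 1 or 2 patient evaluable for escalation by either of two routes. The first is minimum safety evaluation with the whole Cycle 0 dose and "at least 66% of the intended dose of RXC004 during Cycle 1" (in Module 2, also the whole Cycle 1 Day 1 nivolumab infusion). The second is a DLT in Cycle 0 or Cycle 1. SAP VI.J.4 defines its DLT Evaluable Population the same way.

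On replacement, the Cohort Expansion text in 3.1.2 reads "If a patient becomes unevaluable following dose administration they may be replaced", where needed to reach three evaluable patients. Section 3.1.3 adds that a withdrawn, non-evaluable patient is replaced. Neither sentence mentions a DLT ruling. On escalation, 3.1.2 reads "If no DLT is observed in a cohort, then dose escalation may occur".

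The DLT lists differ by module. Module 1 (5.2.6) includes the item "Results in an interruption of dosing schedule of more than 14 days". Module 2 (5.3.6) has no item on interruption length. It has a catch-all, "Is greater than that at baseline, is clinically significant and/or unacceptable, and is judged to be a DLT by the SRC", and an item for related events that meet a protocol stopping criterion.

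For Grade 2 colitis in Module 2, Table 6 interrupts RXC004 until the event is Grade 1 or less and steroids are at or below 10 mg prednisone per day. It adds "If event re-occurs after re-starting study treatment, then RXC004 and nivolumab (if applicable) should be permanently discontinued". Appendix 5 says "If no improvement in 72 hrs despite treatment, treat as Grade 3" and makes restart depend on a steroid taper, in wording that ends "prednisone per day equivalent dose) over at least 1 month".

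SAP IX bases safety analyses on the Safety Population. SAP IX.B includes DLTs as a row of the overall AE summary and as a separate table. SAP VII.C asks for the number of patients in each population. The SAP states no other use for the DLT Evaluable Population.

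**The concern.** Leaving under-exposed patients out of an escalation decision is ordinary practice. It becomes awkward when the under-exposure was caused by the drug. A patient who has to stop RXC004 for a related toxicity below the listed DLT thresholds is informative about tolerability. Yet once 66% cannot be reached, that patient drops out of the escalation count and may be replaced by someone who can stay on treatment. Module 2 leaves the only safeguard to the SRC's discretion, whereas Module 1 makes a long interruption a DLT in its own right.

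The reporting adds to this. In the Safety Population the same patient appears in the denominator of the DLT percentage as a treated patient without a DLT. The primary objective is safety, tolerability and dose definition, and Appendix 5 itself says the combination may carry a higher colitis risk. What is at stake is whether the DLT figure for a combination dose shows, on its face, how many patients could not be assessed because of related toxicity.

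**Working it through.** **Inputs.** Threshold 66% (protocol 3.1.3, SAP VI.J.4). Module 2 Cycle 1: 28 days of daily RXC004 (5.3 and 5.3.5.1), taken as 28 intended doses. Module 1 Cycle 1: 21 daily doses (5.2).

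**Doses needed.**
- Module 2: 0.66 × 28 = 18.48, so 19 doses. Missing 9 leaves 19/28 = 67.9% (evaluable). Missing 10 leaves 18/28 = 64.3% (not evaluable).
- Module 1: 0.66 × 21 = 13.86, so 14 doses. Missing 7 leaves 14/21 = 66.7% (evaluable). Missing 8 leaves 13/21 = 61.9% (not evaluable).

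**Which holds matter in Module 2.** A hold of L days starting on Day d misses min(L, 29 − d) doses. For this to reach 10, L must be at least 10 and d at most 19. Section 5.3.7 permits holds of up to 14 days for related events, and longer ones after discussion with the sponsor. A 14-day hold starting by Day 15 leaves 14/28 = 50%.

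**Comparison with Module 1.** A hold of 15 days or more is a listed DLT there, so only holds of 8 to 14 days starting on Days 1 to 14 are exposed. In Module 2 no hold length is a listed DLT. Copying the Module 1 item across would still miss Module 2 holds of 10 to 14 days.

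**Worked case.** Take Grade 2 colitis that improves on steroids. It is below the Grade 3 thresholds in 5.3.6. Appendix 5 gives a taper of 2 to 4 weeks once symptoms resolve, and at least a month before restart. Even the shortest, 14 days, exceeds 10. Onset by about Day 19 therefore makes the patient non-evaluable unless the SRC declares a DLT.

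**Effect on a cohort.** Three treated patients, one of them held, with no listed DLT: after replacement the count is 0/3 and escalation may occur. If the SRC rules the hold a DLT it is 1/3 and the cohort expands to six.

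**Effect on the reported percentage (hypothetical).** Six evaluable patients with one DLT, plus one held and excluded: Safety Population 1/7 = 14.3%; DLT Evaluable Population 1/6 = 16.7%; counting the held patient as a DLT, 2/7 = 28.6%.

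**Direction of the replacement rule.** Let p be the listed-DLT rate and q the rate of related, unlisted holds of 10 or more doses. Both are assumed; the documents give neither. A 3+3 level clears with probability (1 − x)³ + 3x(1 − x)⁵, where x = p/(1 − q) if held patients are replaced, x = p if they are kept as DLT-free, and x = p + q if all are ruled DLTs.

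| p | q | Replaced | Kept as DLT-free | All ruled DLTs |
|---|---|---|---|---|
| 0.20 | 0.05 | 0.69 | 0.71 | 0.60 |
| 0.20 | 0.10 | 0.66 | 0.71 | 0.49 |
| 0.20 | 0.20 | 0.60 | 0.71 | 0.31 |

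Replacement is slightly stricter than keeping the patient as DLT-free. It is more lenient only relative to ruling the event a DLT.

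**The case against.** The strongest reply is that the 66% rule removes nothing from the DLT count. The held patient has no listed DLT, so was never in the numerator, and excluding that patient is the more cautious of the two options the rules allow. This stands. A reader might infer that the rule makes escalation easier or hides DLTs; the definitions and the table do not support that.

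Second, the SRC already stands between a hold and the next dose. Section 3.2 has it take interruptions into account and document its decisions, 5.3.6 lets it declare a DLT, and escalation is permitted rather than required. Its remit is a separate document, not available here, and may already require such a ruling. This also stands, and it limits the claim to what the protocol and SAP show.

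Third, withdrawals are largely covered. Table 6 allows discontinuation for any clinically significant AE, and 5.3.6 counts a related stopping criterion as a DLT. Colitis that fails to improve in 72 hours is handled as Grade 3 with both agents stopped, and recurrence after restart also stops both. These are arguably DLTs already, so the point is confined to patients held but not withdrawn. If the interruptions in Table 6 were themselves read as stopping criteria, the gap would be narrower still.

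Fourth, a reader might conclude that the report would hide these cases. It would not. SAP VII.C gives population sizes, and SAP IX.A and IX.B give dose modifications with reasons, relative dose intensity bands, TEAEs leading to interruption, and AE listings with relationship and action taken. Most cases could be pieced together. What is missing is the reason for exclusion and a DLT percentage on the matching denominator.

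**Conclusion.** The point holds in a limited form. In Module 2, a related, unlisted toxicity that costs 10 or more of 28 Cycle 1 doses makes a held patient non-evaluable. The visible text allows replacement without anyone having to decide whether the event was a DLT. Separately, the SAP defines a DLT Evaluable Population but, by its general rule, reports DLTs on the Safety Population, which dilutes the percentage.

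Each such patient changes a cohort count by at most one. The figure of 10 assumes 28 intended daily doses. The plan does not say how held or reduced days enter the intended dose; counted in milligrams, restarting at a lower dose would bring the threshold closer.

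The documents do not support the inference that a Module 2 dose was wrongly cleared. SAP Table 2 shows 1 and 1.5 mg given and 2 mg as not applicable. No colitis or hold rate is documented at those combination doses, so no probability is claimed beyond the assumed illustration. Severity: minor to moderate.

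**What to change.** 1. **SAP VI.J.4 and IX.B.** Report the DLT row and the DLT table by dose level on the DLT Evaluable Population. List treated patients excluded from it by reason (related-AE hold, other). Add one sensitivity count that treats as DLTs all patients excluded because a RXC004- or nivolumab-related AE took them below 66% of Cycle 1 RXC004, adding them to numerator and denominator. Use the 66% rule itself for this count, since an over-14-day cut would miss the 10 to 14 day holds.
2. **Protocol 3.1.3, for any further combination cohort or module.** Require a documented SRC DLT ruling before replacing a patient who falls below 66% because of a related AE. Section 3.2 already uses case-by-case SRC review for evaluable patients started on treatment in error. If the SRC remit contains this step, a cross-reference is enough.

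Adding Module 1's over-14-day item to 5.3.6 is a separate trade-off and is not requested.

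The cost is one extra table from data already collected and one SRC step; the tolerability figure may look slightly less favourable. The SAP can be changed until database lock; after that, the table can be added and documented in the study report. Because 2 mg is marked as not applicable, the second item matters only for future cohorts or modules.
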